Description of the National Diabetes Prevention Program (for both conditions). The yearlong NDPP promotes modest weight loss through diet and physical activity. The curriculum is published by the CDC.3 We will follow CDC guidelines for implementing the standard group-based NDPP,³⁷ including 16 weekly to biweekly sessions, followed by ≥6 monthly sessions over a total of one year. The objective of NDPP is achieving ≥5% weight loss. Attending more sessions is associated with greater weight loss, 4,22 and guidelines allow NDPP sites to offer more than the minimum 22 sessions to support this goal. We will offer 25 total NDPP sessions (16 in months 1-6; 9 in months 7-12), held at the same time, day, and location in group visit rooms available at 8 neighborhood primary care clinics. There will also be an option to attend classes virtually via phone or videoconference. In light of COVID-19, in-person group classes will be offered when allowable by public health entities and Denver Health, although a virtual attendance option will remain for participants who prefer to join remotely. Two new NDPP classes will commence quarterly over 2.5 years. To minimize potential contamination, participants in the two study arms will be enrolled in separate NDPP classes. Trained, bilingual lay health educators will lead NDPP classes as Lifestyle Coaches and provide make-up sessions as needed. They will be observed by the research coordinator and/or qualitative research assistant for fidelity and to assess for potential bias in NDPP delivery. Weight is measured at each session on a high-capacity, medicalgrade scale, or by reporting their weight from a study-provided in-home scale. As required by the NDPP curriculum, participants are encouraged to achieve a weekly goal of ≥150 minutes of moderate to vigorous intensity physical activity (beginning gradually as needed). Participants are instructed to track start and stop times and report total weekly activity minutes at the following session. The most recent CDC curriculum also

encourages a low-fat diet, but does not require monitoring of dietary adherence.^{3,32} Lifestyle Coaches conduct support calls between sessions to support engagement and health behavior change, address individual questions and concerns, and remind participants about upcoming sessions.

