General quantitative approaches. Differences in characteristics between study groups will be assessed using chi-square and t-tests to examine potential sampling bias. Percent weight change is the primary outcome, which has a well-documented association with T2D incidence.^{2,20} ITT analyses will include all randomized participants regardless of NDPP participation, including those lost to follow up. Weight loss data for women who become pregnant during the study will be excluded from analyses. Patient-level covariates will be screened in bivariate analyses and included in multivariate analysis if related to the outcome at p<.2, differ between treatment arms, or associated with dropout. Covariates and potential moderators will include age, gender, race/ethnicity, primary language, comorbidities, and other demographic and clinical variables. Although primary analyses examine a single outcome per patient (e.g., percent weight loss), for longitudinal analyses (e.g., perceived risk) we will determine whether missingness patterns are ignorable or nonignorable. 51-54 If so, we will employ likelihood-based methods that use all available data, adjusting for covariates associated with missingness. If missingness is non-ignorable we will use pattern mixture models.⁵⁵ If normality assumptions are not met, we will use transformations to normalize distributions, ordinal or Poisson regression where appropriate, and/or the appropriate link function and distribution (e.g., logit link, gamma distribution). We will use general (generalized) linear mixed models to incorporate data structures that may be both hierarchical (patients within groups) and longitudinal (repeated observations over time). 56,57 Hypothesis tests will be two-sided with α=.05 or p values reported. Goodness of fit statistics and model fitting diagnostics will be used to assess for influential points, outliers, overdispersion, and heteroscedasticity and to evaluate alternative model specifications.⁵⁷ SAS version 9.4 (SAS Institute Inc., Cary, NC) will be used for analyses.

Aim 1: To evaluate clinical effectiveness of the Pre-NDPP intervention.

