Hypothesis 1.1. Pre-NDPP participants will experience greater weight loss than those directly enrolled into NDPP. The primary outcome for this analysis will be percent weight change among all randomized participants. As study participation includes groups of individuals in the same study arm, the data structure will be hierarchical, with patients nested within groups. Statistical models are shown in hierarchical notation below.

Likelihood of achieving ≥5% weight loss in the NDPP will also be evaluated (using generalized linear mixed models with logit link), as well as percent weight change from first to last NDPP sessions attended.

Level 1 model. Individual outcomes will be modeled as a function of patient characteristics (fixed effects), such as sociodemographic variables, baseline BMI, and comorbid conditions: $Y_{ij} = \beta_{0j} + \beta_{1j} X_{1ij} + \beta_{2j} X_{2ij} + ... + \beta_{pj} X_{pij}$ Level 2 model. Group level models specify relationships between group-level predictors and coefficients in the Level 1 model. The intervention effect is included as 0 if control, 1 if intervention: $\beta_{0j} = \gamma_{00} + \gamma_{01}$ (intervention)+ u_{0j} . Thus, for a standardized model, γ_{00} is adjusted mean weight loss for patients in the standard condition (i.e., no pre-session intervention), γ_{01} represents the average increment (decrement) from the mean for groups with intervention patients, and u_{0j} is a group level random effect that reflects between-group variance and is the difference between group means and the predicted mean based on the model, and $u_{0j} \sim N(0,\tau_{00})$. Thus, Hypothesis 1.1 can be tested as H_0 : γ_{01} =0 vs H_1 : γ_{01} ≠0.

Hypothesis 1.2. Pre-NDPP participants will have greater engagement in the NDPP than those who are directly enrolled into the program. The outcome variables, number of sessions attended and days of participation, will be analyzed using similar approaches. If the distribution of outcomes is non-normal we will use generalized linear mixed models with the appropriate distribution and link function, as described above. We will also examine the dichotomous outcome of ≥1 NDPP session attended using multilevel logistic regression (generalized linear mixed model with logit link and random effect for group).

Aim 2: To examine mediators and moderators of Pre-NDPP outcomes.

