Sample size and power. Pre-NDPP pilot data indicate a 0.36 effect size for percent weight change in the NDPP with an intraclass correlation coefficient (ICC) of 1.44%. To be conservative for our primary outcome of percent weight loss among all randomized participants regardless of NDPP participation, we estimate minimum effect sizes detectable for various sample sizes and ICCs (Table 2), with effect sizes of approximately 0.28 to 0.35 for analyses of the primary outcome with a type-1 error rate of .05. Consequently, we expect that 500 randomized participants will provide adequate power while accounting for expected attrition. Note that mediation and moderation analyses are considered exploratory, as estimated power is unknown.

| Table 2: Estimated power to detect treatment differences in percent weight loss. | | | | | |
|--|-----------------------|-----|-----------------------|---|-------|
| Groups per arm | Patients per group | ICC | Effective sample size | Detectable difference (effect size) | Power |
| 10 | 18 (180 per arm) | 1% | 154 | .32 | 80% |
| 10 | 18 (180 per arm) | 2% | 134 | .35 | 82% |

| 10 | 20 (200 per arm) | 1% | 168 | .31 | 81% |
|----|------------------|----|-----|-----|-----|
| 10 | 20 (200 per arm) | 2% | 145 | .33 | 80% |
| 12 | 20 (240 per arm) | 1% | 201 | .28 | 80% |
| 12 | 20 (240 per arm) | 2% | 174 | .31 | 82% |

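### Table 2's 80–82% power allows for the ICC but not for having only 10 or 12 classes per arm; on class-level degrees of freedom it is 75.6–78.9%

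*Combined protocol and SAP*

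**What the plan says.** Section IV.F, Sample size and power, gives Table 2 as the basis for the power of the primary comparison: "we estimate minimum effect sizes detectable for various sample sizes and ICCs (Table 2), with effect sizes of approximately 0.28 to 0.35". It lists six scenarios with ICCs of 1% and 2%, each with an effective sample size, a detectable effect and a power. Two of them read "10 | 20 (200 per arm) | 1% | 168 | .31 | 81"% and "12 | 20 (240 per arm) | 1% | 201 | .28 | 80"%. The section quotes a pilot effect size of 0.36 and a pilot ICC of 1.44%. It does not say which reference distribution produced the power column.

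The design and model are described elsewhere:

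- Section IV.C, Description of the National Diabetes Prevention Program, says that "participants in the two study arms will be enrolled in separate NDPP classes" and that "Two new NDPP classes will commence quarterly over 2.5 years".
- Hypothesis 1.1 in Section IV.F puts the treatment term in the Level 2 (group) equation: "The intervention effect is included as 0 if control, 1 if intervention". The same equation carries a term that "is a group level random effect that reflects between-group variance".
- General quantitative approaches says "We will use general (generalized) linear mixed models to incorporate data structures that may be both hierarchical (patients within groups) and longitudinal" and names SAS 9.4 and two-sided tests at 5%. It names no degrees-of-freedom method.

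**The concern.** Clustering reduces power in two ways. Correlation within classes lowers the effective number of patients, and the small number of classes limits how well the variance between classes can be estimated. Table 2 deals with the first and not the second.

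Because class is nested in arm, the error term for the treatment contrast includes the variation between classes, and only 20 or 24 classes inform it. A t test on 18 or 22 degrees of freedom needs a critical value of 2.10 or 2.07, not 1.96. Table 2 is the only stated basis for the power of the primary test, and the section presents its scenarios as conservative. If the planned test has fewer degrees of freedom than the table assumes, the stated power is too high. With no method named, the choice could also be made after the data are seen.

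**Working it through.** **Inputs.** From Table 2: classes per arm k, patients per class m, ICC and effect size d. From General quantitative approaches: two-sided 5% test. Equal class sizes are assumed, as in Table 2.

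**Step 1. Effective sample size per arm:** n = km / [1 + (m − 1)·ICC]. For row 1, 180 / (1 + 17 × 0.01) = 180 / 1.17 = 153.8.

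**Step 2. Reproduce the stated power.** The noncentrality is δ = d·√(n/2). For row 1, 0.32 × √(153.8/2) = 2.807. The normal approximation gives 80.1%, and a t test on patient-level degrees of freedom (2km − 2) gives 79.9%. All six rows agree with Table 2 to within half a point on either basis.

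**Step 3. Same δ, noncentral t on 2(k − 1) degrees of freedom.**

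| Row (k × m, ICC) | n: table / computed | d | Stated power | Normal | Patient-level t | Class-level t (df) | Shortfall, points |
|---|---|---|---|---|---|---|---|
| 10 × 18, 1% | 154 / 153.8 | .32 | 80 | 80.1 | 79.9 | 75.6 (18) | 4.4 |
| 10 × 18, 2% | 134 / 134.3 | .35 | 82 | 81.8 | 81.6 | 77.4 (18) | 4.6 |
| 10 × 20, 1% | 168 / 168.1 | .31 | 81 | 81.1 | 80.9 | 76.7 (18) | 4.3 |
| 10 × 20, 2% | 145 / 144.9 | .33 | 80 | 80.2 | 80.0 | 75.7 (18) | 4.3 |
| 12 × 20, 1% | 201 / 201.7 | .28 | 80 | 80.3 | 80.1 | 76.6 (22) | 3.4 |
| 12 × 20, 2% | 174 / 173.9 | .31 | 82 | 82.4 | 82.3 | 78.9 (22) | 3.1 |

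**Step 4. Effect detectable with 80% power.** The required δ is 2.963 on 18 df and 2.932 on 22 df, against 1.960 + 0.842 = 2.802 under the normal approximation. Then d = δ·√(2/n). For row 1, 2.963 × √(2/153.8) = .338. The six rows give .338, .362, .323, .348, .292 and .314, against the listed .32, .35, .31, .33, .28 and .31.

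**Step 5. The design as described, with everyone randomized.** Two classes a quarter for 2.5 years is 2 × 4 × 2.5 = 20 classes, or 10 per arm. The 500 participants in the Recruitment section then give 500/20 = 25 per class. At ICC 1, 1.44 and 2%, n = 250/1.24 = 201.6, 250/1.3456 = 185.8 and 250/1.48 = 168.9. On 18 df the detectable effects are .295, .307 and .322. Table 2 has no such row.

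**Step 6. Power at the pilot values (d = 0.36, ICC 1.44%) on 18 df.** For 10 × 25, δ = 0.36 × √(185.8/2) = 3.470 and power is 90.7%. For 10 × 20 (400 analysed), n = 200/1.2736 = 157.0, δ = 3.190 and power is 85.4%.

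**Step 7. What the df choice does to the test.** Balanced normal data were simulated for the six rows, 400,000 runs each. The class variance was estimated as zero in roughly 17 to 36% of runs.

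| Analysis | Power, % | Type I error, % |
|---|---|---|
| Class-level df, variance not truncated at zero | 75.6–78.9 | 5.0 |
| Class-level df, variance truncated at zero | 73.8–78.5 | 3.7–4.4 |
| Patient-level df, variance truncated at zero | 78.0–81.5 | 5.0–5.7 |

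**The case against.** **Table 2 is not miscalculated.** Every effective sample size and every power figure reproduces, and the lower figures appear only after a reference distribution is substituted that the plan does not name. This stands as a description: the fault is an omitted small-cluster correction, not a slip of arithmetic. It does not rescue the stated power, because the plan's own nesting and Level 2 test point to class-level degrees of freedom.

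**Patient-level degrees of freedom nearly recover the stated power.** They do, at 78.0 to 81.5%, but Type I error then reaches up to 5.7%. A reader might infer that an unnamed method puts the validity of the test at risk. The simulation does not support that, since error stays close to 5% either way.

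**Covariate adjustment could make up the loss.** The model adjusts for baseline characteristics. To bring each row back to 80% at its printed effect, covariates would have to remove between 1 − (.31/.314)², about 3%, and 1 − (.32/.338)², about 10%, of the outcome variance. That is possible, but the documents give no R-squared and Table 2 claims no such gain.

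**The printed effects are rounded.** At the upper rounding limit (d + .005) the last row reaches 80.2%. The other five stay below 80%.

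**The general claim about detectable effects largely survives.** The restated rows span .292 to .362. For 10 classes per arm with 20 or 25 patients, the values at ICC 1 to 2% (.295 to .348) lie inside the stated approximate range.

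**Conclusion.** The concern holds in a limited form. Table 2's power is overstated by 3.1 to 4.6 points for the class counts it uses, and all six rows fall below 80% on class-level degrees of freedom. This rests on equal class sizes, the tabulated ICCs, no credit for covariates, and a test of the kind written under Hypothesis 1.1.

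Two stronger readings are tempting, and the documents support neither.

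- *The trial is underpowered.* At the pilot effect and ICC, power on 18 degrees of freedom is 85.4 to 90.7%, so the target of 500 stands.
- *The plan contradicts itself on the number of classes.* The programme description fixes two classes a quarter, hence 10 per arm. The Pre-NDPP description, which assigns coaches one class of each type per quarter, can be read collectively and then agrees. Table 2's 12-per-arm rows are scenarios, since the text says it varies the sample size.

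The unnamed degrees-of-freedom method would on its own be a missing detail. It matters here because it decides which power figures apply.

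**What to change.** 1. Restate Table 2's power and detectable effects on 2(k − 1) degrees of freedom, using the values in Steps 3 and 4, and say under the table which reference distribution was used.
2. Add the row for the planned design with all randomized participants: 10 classes × 25 per arm, detecting .295, .307 and .322 at ICC 1, 1.44 and 2%.
3. Under Hypothesis 1.1, state that the intervention effect in the primary mixed model is tested on between-class degrees of freedom, including when the class variance is estimated as zero.

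This costs a revised table and one sentence, with no extra patients. The stated power becomes slightly less favourable. Keeping class-level degrees of freedom when the variance estimate is zero also makes the test mildly conservative at these low ICCs: Type I error is about 4% and power is up to about 2 points below the restated values (Step 7).

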
III. Preliminary Studies/Progress Report

Preliminary data. Our pilot study was conducted at Denver Health (DH), a safety net healthcare system and early NDPP adopter, offering the program since March 2013 per CDC-established guidelines.⁷ Bilingual lay health educators received CDC-approved training to serve as NDPP coaches. New NDPP classes began every 3-6 months in DH primary care clinics, in English and Spanish. We used CDC-established NDPP eligibility criteria (e.g., A1c 5.7-6.4).³⁷ Eligible individuals were identified from medical records and referrals and enrolled through outreach calls, without fees or financial incentives to participate. Following standard NDPP delivery to 1,065 participants through July 2016 cohorts, we found disconcerting evidence of disparities in outcomes, consistent with national data⁴ (e.g., only 27% of NHBs with ≥2 recorded weights achieved the ≥5%

weight loss goal in national data, comparable to 23% of NHBs at DH). Thus, we aimed to develop a cost-effective NDPP adaptation by adding an educational and motivational "pre-session" before enrollment. NDPPs launched in September 2016 and January 2017 were preceded by these group-based meetings. In brief, participants received education on diabetes risks and information about locally available resources to reduce risk, including the NDPP. Coaches used MI techniques to help participants identify their preferred plan of action to reduce risk, such as attending the NDPP, and guided participants in identifying barriers and possible solutions to enable participation. Seventy-five participants completed a pre-session before NDPP enrollment. Another 15 individuals (17%) attended a pre-session, but did not enroll, and no further data were collected.

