Analysis. Pilot study outcome measures were duration (days) and intensity (percentage of sessions attended) of NDPP participation, percent weight change (based on weight at first/last NDPP sessions attended), and achievement of ≥5% (vs. <5%) weight loss at any point in the program (per Centers for Medicare and Medicaid Services [CMS] performance standards¹0). The primary analysis for this longitudinal cohort study compared outcomes of 75 participants who received a pre-session prior to the NDPP to 1,065 previously enrolled DH participants who did not. We also conducted a sensitivity analysis comparing outcomes of the 75 pre-session participants to outcomes of 42 participants who began the NDPP during the immediately preceding June 2016 cycle, but were not offered a pre-session. This group was selected for the sensitivity analysis to reduce potential influences of differences over time in coaching staff, other modifications in NDPP implementation (e.g., incorporating the revised 2016 NDPP curriculum³), and general time trends. Differences in characteristics between intervention groups were assessed using chi-square and t-tests. Differences in NDPP outcomes were analyzed with ANCOVA and multivariable logistic regression. Covariates included age, gender, race/ethnicity, and income (≥/< 133% of federal poverty level).

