Recruitment. We will identify potential participants through referrals from healthcare providers at DH, which is known to support initial enrollment in the NDPP.²¹ Providers refer through the electronic health record (EHR) per usual practice. Since 2013 over 7,000 at-risk patients were referred by providers to the DH NDPP. If needed to meet recruitment goals, we will also identify participants from a risk registry based on EHR data, which has previously identified over 10,000 NDPP-eligible patients annually. The enrollment process after initial identification will be as follows: 1) Lifestyle Coaches pre-screen via medical record review and contact referrals by phone to verify interest, eligibility, and schedule eligible individuals for an initial screening visit (held in-person or remotely as needed), 2) consenting individuals are randomized to receive Pre-NDPP or usual care NDPP (note we will use Denver Health's e-consent process for any virtually-conducted recruitment visits), and 3) complete an initial assessment (behavioral and anthropometric assessments), 4) the Pre-NDPP group completes a pre-session 1-2 weeks before NDPP classes start, 5) both groups complete a follow up behavioral

assessment 1-2 weeks before NDPP classes start (collected in-person or remotely as needed), and 6) both groups commence yearlong NDPP classes (held in-person or remotely as needed).

We will initially enroll 500 participants, with a goal of 400 randomized participants across both groups attending ≥1 NDPP session as based on statistical power estimates (see Sample Size and Power Calculations below). From previous experience, we expect approximately 50% of referred patients to express interest in participating upon initial outreach. Then after initial assessment, we expect early attrition of approximately 20% of consenting participants. We will seek to recruit 50 individuals every 3 months, for a total of 500 participants recruited over 2.5 years (i.e., 200 participants annually). From 2013-2017, we recruited 300 NDPP participants on average each year. Thus, we expect to fully meet RCT recruitment goals. Demographic characteristics of individuals in this study are expected to approximately match characteristics of all previous NDPP participants at DH: 78.0% female, 58.2% Hispanic, 19.5% NHB, 21.0% NHW, 61.4% low-income (including a majority of low-income individuals within each racial/ethnic group), and a mean age of 48.4 (SD=12.7) years.

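### Adequate power for the ITT primary outcome is asserted rather than shown: no expected ITT effect is set against Table 2, the table does not describe the planned classes, and its 80–82% falls to about 76–79% on class-level degrees of freedom

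*Combined protocol and SAP*

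**What the plan says.** Section IV.F (Sample size and power) opens with the pilot: "Pre-NDPP pilot data indicate a 0.36 effect size for percent weight change in the NDPP", with an ICC of 1.44%. It then recognizes that the primary analysis takes in everyone randomized, whether or not they attend. For that reason it does not power at 0.36 but tabulates minimum detectable effects, "with effect sizes of approximately 0.28 to 0.35 for analyses of the primary outcome with a type-1 error rate of .05". From these it concludes that 500 randomized gives adequate power after attrition.

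The pilot outcome is defined in Section III (Analysis): "percent weight change (based on weight at first/last NDPP sessions attended". Its pre-session group was the 75 people who went on to enroll; "Another 15 individuals (17%) attended a pre-session, but did not enroll, and no further data were collected". The trial's primary outcome (Sections IV.A and IV.F) is percent weight change from baseline to 12 months in all randomized participants.

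On layout, Section IV.C says "Two new NDPP classes will commence quarterly over 2.5 years", with the arms in separate classes and 50 people recruited each quarter. Recruitment is set at 500, "with a goal of 400 randomized participants across both groups attending ≥1 NDPP session as based on statistical power estimates", with early attrition of about 20% expected. Under Hypothesis 1.1 the model enters the intervention at group level, with a random effect for group. Section IV.F adds: "Hypothesis tests will be two-sided with α=.05 or p values reported".

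**The concern.** A list of detectable effects shows adequate power only when it is compared with an effect the trial can expect. The plan gives no such effect for the ITT analysis. The one estimate it cites differs from the primary outcome in population (enrollees against all randomized) and in time window (first to last session against baseline to 12 months).

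The rows of Table 2 are also not the trial's rows, and its power figures do not use the reference distribution that a group-level intervention effect calls for. If the stated power is higher than the design delivers, a null result would be read as stronger evidence of no benefit than it is.

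**Working it through.** **Inputs.** Two-sided α = 0.05; pilot effect 0.36 and ICC 1.44%; Table 2 (IV.F). 500 randomized 1:1, 50 per quarter, two classes per quarter for 2.5 years, about 20% early attrition (IV.C). Pilot mean weight loss 3.4% and 1.5% (III, Results).

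**Formulas.** With k classes per arm, m people per class and standardized effect d:
- effective sample size per arm, ESS = k·m / [1 + (m − 1)·ICC];
- noncentrality = d·√(ESS/2);
- power from the normal distribution, or from the noncentral t with 2k − 2 df when arm is tested between classes (18 df for k = 10, 22 df for k = 12).

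**Step 1: reproduce Table 2.** First row: 180/(1 + 17 × 0.01) = 153.8, stated as 154; 0.32 × √(154/2) = 2.81; normal power 80.2%.

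| Classes × size per arm | ICC | ESS stated | Effect stated | Power stated | Normal | Class-level t |
|---|---|---|---|---|---|---|
| 10 × 18 | 1% | 154 | .32 | 80% | 80.2% | 75.7% |
| 10 × 18 | 2% | 134 | .35 | 82% | 81.7% | 77.3% |
| 10 × 20 | 1% | 168 | .31 | 81% | 81.1% | 76.6% |
| 10 × 20 | 2% | 145 | .33 | 80% | 80.2% | 75.7% |
| 12 × 20 | 1% | 201 | .28 | 80% | 80.2% | 76.5% |
| 12 × 20 | 2% | 174 | .31 | 82% | 82.4% | 78.9% |

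The table is internally correct for a large-sample test (a t with 2·ESS − 2 df agrees as well). On class-level df every row falls below 80% at its own stated effect. This step needs no assumption about dilution.

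**Step 2: compare the rows with the planned layout.** Two classes per quarter × 10 quarters = 20 classes, or 10 per arm. Fifty recruits per quarter over two classes = 25 randomized per class. No row is 10 × 25. Both 12-class rows fall outside the layout, and one of them holds the only 0.28.

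**Step 3: the planned layout, 10 × 25 per arm, all 12-month weights obtained.** At ICC 1.44%, ESS = 250/(1 + 24 × 0.0144) = 185.8.

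| ICC | ESS | Detectable at 80%, normal | Detectable at 80%, 18 df |
|---|---|---|---|
| 1% | 201.6 | 0.279 | 0.295 |
| 1.44% | 185.8 | 0.291 | 0.307 |
| 2% | 168.9 | 0.305 | 0.322 |

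**Step 4: an illustrative ITT effect.** If 20% do not attend and gain nothing, attendance is equal in the two arms and the SD is unchanged, d = 0.80 × 0.36 = 0.288. Only the 20% comes from the plan; the other three are assumptions. Because non-attenders stay in this analysis, the matching sample is 250 per arm.

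| ICC | Normal | 18 df |
|---|---|---|
| 1% | 82% | 78% |
| 1.44% | 79% | 75% |
| 2% | 75% | 71% |

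Attendance of 70% to 90% gives d = 0.70 × 0.36 = 0.25 to 0.90 × 0.36 = 0.32, and power of 63% to 84% (18 df, ICC 1.44%, all weights).

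**Step 5: sensitivity to missing weights.** With 0.288 and only 200 weights per arm (10 × 20, ICC 1.44%), power is 72% (normal) or about 68% (18 df).

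**The case against.** The strongest reply is that the plan is more careful than a quick reading suggests. It cites 0.36 as a pilot reference, says that the ITT population differs, and moves to smaller effects for that reason. Table 2 contains no arithmetic slip. Both points stand.

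A reader might set 0.288 against Table 2 and infer that five of its six rows are underpowered. That does not follow. The effect is diluted only if non-attenders stay in, which means 250 per arm, not the 180 to 240 in the table. If they left the analysis, the effect would stay at 0.36 with 200 per arm, and power would be 87–91% (normal); but that is not the declared ITT analysis.

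A reader might also infer a true power of about 68%. That requires dilution plus the loss of 100 of the 500 weights, which the plan does not assume. It schedules and pays for a 12-month weight in all randomized participants, supplies home scales and plans imputation. The 20% is early attrition, not missing 12-month weights.

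The illustrative effect could also be larger:
- Equal attendance runs against Hypothesis 1.2. With an assumed 83% against 77%, and no weight change in non-attenders, the difference is 0.83 × 3.4 − 0.77 × 1.5 = 1.67 points. Dividing by the implied SD of 1.9/0.36 = 5.28 gives d = 0.316 and power of 86% (normal) or 82% (18 df) at ICC 1.44%.
- Non-attenders share no class, so the ICC may dilute too. At 0.64 × 1.44%, power at 0.288 is 83% or 79%.
- Covariate adjustment may help.

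In the other direction, a 12-month weight may show a different effect from a last-session weight.

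Finally, the plan names no df method, so 18 df is a reviewer's choice. It follows from a group-level intervention term and 20 classes, and the plan offers no reason for a large-sample test.

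What remains after all this is that the plan makes none of these comparisons itself.

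**Conclusion.** The point holds as a gap in justification plus a modest overstatement of power. Three parts rest on the documents alone: no expected ITT effect is compared with Table 2; the table lacks the 10 × 25 layout and includes 12-class rows that the schedule does not produce; and the goal of 400 people attending at least one session is not the ITT denominator. A fourth part, that the table's 80–82% becomes about 76–79%, rests on testing arm between classes with 18 or 22 df.

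For the planned layout with complete weights, the detectable effect on 18 df is about 0.295 to 0.322 across ICC 1% to 2%. The 71–78% power at 0.288 is illustrative and depends on the three unstated assumptions in the working. It is borderline, with no room for missing weights.

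The documents do not support saying that the trial is underpowered, that 0.36 was its design effect, or that Table 2 is miscalculated on its own terms.

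**What to change.** - Recompute Table 2 for 10 classes per arm and 25 randomized per class at ICC 1, 1.44 and 2%, using class-level df, with full and with reduced 12-month weight completion. Name the df method in the analysis plan.
- Remove the 12-class rows, or explain how the schedule yields 12 classes per arm.
- State the expected ITT effect, its assumptions (attendance by arm, effect in non-attenders, SD, 12-month against last-session weight) and a range of about 0.25 to 0.32.
- Replace the statement of adequate power with the resulting figures as a range, not a single number.
- Express the retention goal for the primary outcome as 12-month weights obtained; keep attendance of at least one session as an engagement target.

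This changes text and one table only, with no added enrollment. The cost is that the stated power and detectable effect become slightly less favorable.
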